#### Acute Postoperative Assessments (total time approximately 30 min):

**(1) Pain Intensity:** The 11-point NRS pain intensity will be recorded every 4h for 0-72h postoperatively of the operated knee, then twice daily thereafter until discharge. The area-under-curve (AUC) for NRS over 0-72h will be calculated and interpreted as the burden of acute postoperative pain.

**(2) Neurophysiologic Assessment of mechanical (punctate) hyperalgesia and hypoalgesia** will be performed at least 6 hours after removal of epidural, post-incision by the RN under the supervision of PI. The elasticized (ACE) wrap around the knee will have already been removed at 24h post-incision. With the subject in a relaxed supine position with eyes closed, stimulation with a hand-held von Frey filament (4 g) will begin on the lateral aspect of the knee where the patient reports no pain sensation (Figure below), and move in 2 cm steps toward the incision until the subject reports a distinct change in sensation. The first point where the subject reports the sensation as 'painful', 'sore', or 'sharper', will be marked with an alcohol pen. To map the area of this mechanical sensitivity around the knee, testing will be done every 2.5 cm around the mid-line along radial lines. If no change in sensation is found, stimulation will be stopped at 5 cm from the surgical incision to restrict our testing to the area of **secondary mechanical hyperalgesia**. Any areas of numbness will also be noted. To quantify the area, a transparent plastic sheet with pre-marked grid marks will be placed over the knee to facilitate the transfer of the skin markings to our template. The area will then be measured with a digital planimetry software.

(a): In preliminary studies we found the mean area to be 37 cm^2. Areas of numbness will also be noted.

**(3) Functional Measures (ROM only):** The active and passive ROM of the knee will be recorded every day in the hospital by the physical therapist. In addition, the RN will measure active and passive ROM at least 6 hours

after removal of epidural, (performed at the same time as assessment of mechanical (punctate) hyperalgesia and hypoalgesia.

**Discharge from hospital:** Patients will be discharged from the hospital with the same oral opioid medications used in the post-operative period. Prior to discharge, patients will be given a questionnaire (one for each wk, to be mailed to PI in pre-paid envelope weekly) to record analgesics consumed during the first 3 wks postoperative period. For the first 3 wks after surgery, patients will be contacted by e-mail, telephone or facsimile on a weekly basis and queried about NRS pain intensity and medications used by the RN. Serious adverse events will be reported to the PI and the orthopedic surgeon.

**Postoperative Follow-up and Outpatient Management:** At 3 and 6 wks after surgery, patients will return to the orthopedic surgeon (Orthopedic Building) for follow-up. At their visit, the functional assessments noted below and analgesic consumption questionnaires (if not previously mailed in) will be collected by the RN, after which patients will be given new analgesic consumption and functional assessment questionnaires. Their oral opioids will be gradually weaned and converted to NSAID or cyclo-oxygenase (COX)-2 inhibitor (celecoxib 200 mg) daily and tramadol hydrochloride 50 mg tablets as required, with a maximum of 6/day. The outpatient physical therapy data from the time the patient was discharged to the 3 wk visit will be collected. The results of the knee radiographs at follow-up visits will be collected. Over the 3 wk to 3 mo postoperative period, study patients will be contacted by email, telephone, or facsimile by the RN, at 10-14 day intervals, and queried about NRS pain intensity, medications used, and any adverse events.

Coinciding with the orthopedic surgeon visit at 3 mo, the functional assessments and analgesic consumption questionnaires will be collected by the RN. They will then be given new analgesic consumption and functional assessment questionnaires, and new prescriptions for analgesic drugs if needed (NSAIDs or COX-2 inhibitor). Over the 3 to 6-mo postoperative period, they will be contacted by email, telephone, or facsimile, every 20-30 days and queried about NRS pain intensity, medications used. A full analgesic treatment protocol as mentioned above will be followed for all patients in the study. At 6 mo, patients will return to the Orthopedic Building for their final visit at which time the functional assessments, BDI, and analgesic consumption questionnaires will be collected by the RN, and they will undergo a knee radiograph. An additional questionnaire, the SF-MPQ-2, will be administered at 6 mo to better characterize the subject's sensory qualities of pain. In addition, they will return to the Department of Anesthesiology Clinical Research Section (Room 1487 Jelke) for *examination of the knee for peripheral neuropathic pain (StEP)* and ROM measurement (total time approximately 1 hour), as was performed pre-surgery. At this time we will collect the third and final 5mL RNA blood sample.

#### **Long-term Assessments (same methods used pre-surgery):**

(1) **Pain Intensity:** NRS of the operated knee will be obtained by RN from the patients at the 3 wk, 6 wk, 3 mo and 6 mo scheduled visits.

(2) **Neurophysiologic Assessment** will be performed at the 6 mo scheduled visit.

(a) *Examination of the knee for peripheral neuropathic pain (StEP)*

(3) **Psychosocial Measures:** Beck Depression Inventory will be administered at 6 mo by RN.

(4) **Functional Measures:** ROM, WOMAC and SF-36 questionnaires will be administered at 3 wk, 6 wk, 3 mo and 6 mo.

(5) **Skin Temperature:** Skin temperature will be performed at 6 months

**Patients who have NRS $\geq$ 4 at three wks and beyond:** For patients having NRS $\geq$ 4 at 3 wk and beyond, the oral opioid regime will be continued. If the hydrocodone/acetaminophen regime does not maintain a NRS $<$ 4, then oral long-acting opioids such as time-release oxycodone 10 mg twice/day will be prescribed. The purpose of closely following the analgesics and NRS for the study patients is to ensure that at the 6-mo time point the analgesic consumption is within a standard protocol for all patients, whether they do or do not have PPP. Patients who have persistent pain at the 3 and 6-mo visits will be evaluated by the orthopedic surgeon for prosthetic-related failure. An examination will be performed to evaluate instability of the tibial femoral joint or patellar maltracking. Plain radiographs will be reviewed by the orthopedic surgeons (Co-investigators) for evidence of prosthetic loosening, malposition and patellar maltracking, as well as overall axial alignment to ensure coronal alignment is within the range of neutral to 10 deg of valgus. If this evaluation is negative, an erythrocyte sedimentation rate (ESR) and C-reactive protein (CRP) measurement will be obtained as a screening tool for infection. If these indices are abnormal (ESR $>$ 30 mm/h; CRP $>$ 10 $\mu$ g/mL), an aspiration of the knee will be performed, including a synovial fluid white blood cell count with differential and culture to rule

out infection. These parameters are based on previous work by [name] (Co-investigator) in this specific topic.

**Statistical Analysis:** *Power analysis and sample size calculation:* The sample size calculation was based on power estimates using our preliminary data on how acute postoperative pain contributes to PPP using the SAS "powerlog" macro. An updated analysis of our multi-center (three) chronic pain after total knee and hip arthroplasty survey study, evaluated one yr postoperatively, provided data for sample size calculation. The one yr follow-up data from this survey provides a conservatively estimate for the incidence of PPP at 6 mo, our primary outcome. To evaluate the effect of acute postoperative pain on incidence of PPP, our multi-center data was stratified based on chronic pain using our PPP criteria. Across the three centers, 259 TKR patients fell within criteria, of which 46 (17.8%) were identified with PPP at one year after surgery. Using a logistic regression, the acute postoperative NRS pain intensity was significant ( $P=0.0005$ ) with an odds ratio of 1.24 for each 1 point increase in acute postoperative NRS pain (95% Wald Confidence limits: 1.098-1.390). The average acute postoperative NRS pain for the entire sample was 5.5 (SD=2.9). Using the data to estimate predicted probability of PPP at the mean acute postoperative pain level, we have an incidence of 15.5% at the mean and 30.3% at the mean plus one standard deviation (NRS=8.4). A power analysis with 90% power and alpha of 0.05, using a logistic regression with no other covariates gives us a required sample size of 130. However, because we plan on utilizing multiple covariates, we estimate the multiple squared correlations at 0.5, raising our sample size estimated to 259. With a 15% dropout rate this values climbs to 298 (round to 300).

**Blinding of data:** To reduce bias, each co-investigator will only be involved in measurements specifically related to their specialization (Pain, Neurophysiologic, Psychosocial or Functional outcomes) and no others.

**Data collection and management:** Data will be collected on a series of password-protected Microsoft Excel worksheets, with data access limited to research personnel. Data will be imported from the Excel sheets and stored as a database using the SAS statistical analysis system on the statistician's workstation where all analysis will take place. The workstation is password protected, with key information encrypted and managed by the biostatistician on his own network, protected by router and software based firewalls. Data will be encrypted (AES 256-Bit) and backed up bi-monthly onto DVD's and will be stored in a locked cabinet in the biostatistician's office. Data will be indexed by a subject identification number. Each subjects' identifying information (name, telephone number) will be recorded in a separate password protected database, indexed by subject ID number, and will not be used in any analyses.

**General statistical analysis:** Descriptive statistics will be reported as mean and standard deviation (SD) for continuous normally-distributed variables, and reported as counts and percentages for dichotomous variables. Assumptions will be evaluated and, if violated, either corrective measures will be taken (data-transformation) or other less restrictive methods will be implemented. Error inflation for multiple pre-planned comparisons will be corrected by using the Bonferroni step-down method. Models will be examined with no risk factors, with individual risk factors, and with multiple risk factors. The distribution of the primary outcome, NRS pain scores at 6 mo, will be evaluated, transformed to normal and then modeled as a continuous variable. If this is not possible, *then the dichotomous version*, as defined for PPP, will be used. We expect that the primary outcome of PPP (dichotomous) will be modeled using a logistic regression because the distribution of NRS pain scores from our preliminary survey data was strongly bi-modal (modes:0, 3). Thus it appears that this kind of distribution represents two distinct populations (a normally distributed pain population and a unimodal 'no-pain' population). Pain intensity (continuous) will be separately modeled for those patients who report a non-zero pain level. Risk factors will be evaluated, for **independent** association with the outcome variable, first for linearity and then for model fit using backward stepwise logistic regression (criterion  $P<0.05$ ). Model fit will be assessed by the Hosmer-Lemeshow test and validity of the fit models and predictive accuracy will be assessed using bootstrapping methods as well as the AUC 'c-index'. Analysis will also be performed on the raw NRS score (at 6 mo) using general linear models and mixed model regression as this may elucidate additional details about relationships among the factors and how they relate to pain at 6 mo. **Mediation** models will be evaluated based on techniques pioneered by Baron and Kenny, but with the modification of bootstrapping techniques to produce multiple mediator results with confidence intervals. Sobel method and  $R^2$  effect-size measures will be used to test and evaluate the mediation effects as well. Distributional assumptions and

model fit will be evaluated for all models. **Moderating** effects will be tested using model building with predefined interactions for linear or logistic models.

Due to the extensive monitoring designed into our protocol we do not expect a large amount of missing data; however, the missing data that does arise will be handled using multivariate multiple imputation. Data not assumed to be missing at random, will be evaluated for systematic effects using sub-groups stratification. Statistical analyses will be performed using SAS version 9.1 (SAS Institute Inc, Cary, NC) or SPSS (SPSS for Windows, Rel. 16.0.1. 2007. Chicago: SPSS Inc.), with statistical significance determined with a Type I error threshold of  $\alpha = 0.05$ . For continuous outcome mediation analysis we will use a SAS macro (INDIRECT macro) and for dichotomous outcomes the SPSS macro version (INDIRECT macro) will be used, as the SAS macro version does not allow for dichotomous outcome variables.

**Primary endpoint:** The *primary endpoint* for the **Primary Aim** will be the incidence of PPP after TKR (similar to our power analysis), evaluated at 6 mo. For the **Secondary Aims**, the *primary endpoint* will be functional outcomes (ROM, WOMAC, SF-36,).

**Secondary endpoints:** The *secondary endpoint* for the Primary and Secondary Aims will examine additional parameterizations of PPP at 6 mo (NRS pain non-dichotomous, StEP neuropathic pain examination). Use of raw NRS pain scores may highlight functional (e.g. linear) relationships between pain and the predictive factors. Analysis will be performed as described for the primary outcome variable (incidence of PPP) but with the re-parameterized outcome variable and different model assumptions, depending on distributional properties. Each re-parameterization will be evaluated with respect to and compared with the primary outcome.

**Covariates:** Preoperative covariates included are as follows: age, weight/BMI, OA severity and ASA status. Perioperative covariates include: postoperative analgesic consumption and duration of surgery. Complications after TKR will be recorded and included as a summed incidence. Patient questionnaires of drug use in the first three wks postoperatively will be converted to daily morphine equivalents and included as a covariate in the predictive models. Although the protocol stipulates uniformity in medication use during the acute postoperative period, once the patient leaves the hospital, their analgesic use over the next 6 mo cannot be rigidly controlled. To reduce variation we will prescribe analgesics as needed (per protocol above mentioned) and will remain in contact with the patients to record additional medication.

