## Approach

**Overall Strategy:** The primary aim of this application is to investigate relationships of risk factors to the development of PPP at 6 mo following TKR, through independently predictive and mediated models. These risk factors are preoperative thermal pain sensitivity, pain anxiety and catastrophizing; postoperative area of secondary mechanical hyperalgesia or hypoalgesia (numbness) and pain intensity. **PPP** for this study will be defined as "**pain in the operated knee at six months after TKR, with other causes of pain excluded and reported intensity on 0-10 NRS scale of  $\geq 4$ .**" The study will also evaluate the relationship of PPP incidence with the severity of functional impairment. This is a single-site prospective clinical investigation of 300 consented OA patients undergoing primary, unilateral TKR. Although we realize the importance of genetic susceptibility on the development of PPP, the complexity of determining the multiple genes that may contribute to this condition is beyond the scope of this proposal. However, prior to surgery we will obtain a blood sample (8.5 mL) from all patients, process it for DNA analysis, and store at -80° C for future studies by [name], NINR (letter of support) to screen for genetic predictors of PPP, such as COMT and GCH1. We will also obtain three blood samples (5ml each) for RNA analysis. In a previous IRB approved study, we also obtained blood samples for RNA analysis prior to hip replacement surgery and 24 hours afterward and found that IL18R1 was up-regulated while IL-8RB was down-regulated and may be related to the normal acute post

operative inflammation. However, we now need to examine the changes in cytokine gene expression in the TKR patients. All of the blood samples will be sent for analysis to [name] laboratory. The patients' genetic information will stay confidential, and will be identified by a study number, and not a name. This information will not be disclosed to any other third party. Personal data will be stored at Rush University Medical Center. The samples sent to [name] laboratory will be appropriately coded so that the patient's name does not appear on the samples. Data will be kept for 1 year from the time the last patient is enrolled in the study.

Study Calendar	Preop	Post-Incision				Post-operative			
		24h	36h	48h	72h	3 wk	6 wk	3 mo	6 mo
General Physical Examination	X					X	X	X	X

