**Enrollment & Pre-surgery Assessments:** Prior to pre-operative assessments, up to 8 weeks prior to surgery, written informed consent will be obtained. Demographic data such as age, BMI, ASA status and a physical examination will be performed by PI and RN. All of the assessments below will be coordinated by the RN, in conjunction with the routine preoperative laboratory tests for undergoing TKR. We will obtain an 8.5mL DNA blood sample as well as a 5mL RNA blood sample. A knee radiograph (AP and lateral weight bearing views) will also be reviewed by the study's orthopedic surgeon to determine OA severity (scale) and documented. Patients will be instructed to discontinue non-steroidal anti-inflammatory drugs (NSAIDs) a wk prior to surgery as routine clinical practice. A prescription for tramadol hydrochloride 50 mg tablets with a maximum of 3 tablets /day will be provided to the patients to be taken if the pain in the knee is of moderate-to-severe intensity prior to the surgical date.

All measures selected for this study are established, reliable and validated and listed in order of importance. These measures will be classified into Pain, Neurophysiologic Assessment, Psychosocial and Functional test categories and may be used as predictors, mediators, moderators, or outcome measures, depending on specific hypotheses, and will be assessed at various time points as shown in the study calendar.

**(1) Pain Intensity: Numerical Rating Scale (NRS) of pain intensity:** The NRS score has been selected as the primary instrument to quantify pain intensity. Subjects will be presented by the RN with 11-point NRS, (0 = "no pain" and 10 = "worst pain imaginable"), accompanied by the instructions "Please rate your pain by

indicating the number that best describes your pain on average in the past 2h of the affected knee joint." The NRS will be evaluated at rest, and also with movement (patient-initiated flexion). The NRS is used extensively in clinical trials reported in the orthopedics, pain and surgical literature. Within the pain literature, a NRS <4 is considered mild pain, while a NRS ≥4 is moderate-to-severe pain.

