#### Potential Difficulties and Limitations

1. We have no way of directly assessing minor nerve damage following TKR.
2. Patient may decide to undergo another elective joint replacement procedure during the 6-mo postop period
3. Although power analysis is based on 17.8% PPP incidence, TKR procedures may vary over the 3-yr duration of study. However our power estimates are conservative and our multivariate analyses are robust and powerful.
4. 6 mo assessment of PPP can be complicated by opioid use in some patients. However, this factor is considered as a covariate in the analysis.

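### Opioids are continued or stepped up to hold NRS below 4, the cut-off that defines PPP, and no 6-month opioid variable is specified, so opioid-controlled persistent pain is counted as no PPP

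*Combined protocol and SAP*

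**What the plan says.** **Outcome.** The Overall Strategy paragraph under Approach defines PPP as "pain in the operated knee at six months after TKR, with other causes of pain excluded and reported intensity on 0-10 NRS scale of" 4 or more. The Pain Intensity item gives the reason for the cut-off: "a NRS <4 is considered mild pain, while a NRS ≥4 is moderate-to-severe pain". The same item asks for average pain over the preceding two hours, so the score is pain under whatever analgesic is then acting.

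**Treatment.** Under Long-term Assessments, the paragraph on patients with NRS of 4 or more from three weeks says that for them, "at 3 wk and beyond, the oral opioid regime will be continued". It goes on: "If the hydrocodone/acetaminophen regime does not maintain a NRS" below 4, "then oral long-acting opioids such as time-release oxycodone 10 mg twice/day will be prescribed".

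**Promised remedy.** Item 4 of Potential Difficulties and Limitations accepts that opioid use can complicate the 6-month assessment and answers that "this factor is considered as a covariate in the analysis".

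**Covariates actually specified.** The Covariates paragraph has a generic item for analgesic consumption after surgery, listed as perioperative, and one outpatient item: "Patient questionnaires of drug use in the first three wks postoperatively will be converted to daily morphine equivalents". The acute pain management section adds analgesics given over 0-72 h. The Covariates paragraph also says that use over the following six months cannot be tightly controlled and that additional medication will be recorded, but it makes no covariate of it.

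**Data.** The study calendar and the 6-month visit text both include an analgesic consumption questionnaire at 6 months.

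**The concern.** The treatment target and the outcome cut-off are the same number. Opioids are continued or increased until the score falls below 4, and a score below 4 at 6 months is then read as absence of PPP. A pain-free patient on no drug and a patient at NRS 3 on a long-acting opioid become the same non-case. PPP incidence is the primary endpoint of the Primary Aim, so the classification feeds the Hypothesis 1 regressions, the Hypothesis 2 mediation models and the prediction equation. The plan recognises the difficulty, but the remedy it names is not defined and is of the wrong kind.

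**Working it through.** **1. Is a 6-month opioid covariate specified?**

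| Where | Analgesic variable | Window |
|---|---|---|
| Acute pain management | analgesics given in hospital | 0-72 h |
| Covariates | generic item, classed as perioperative | not stated |
| Covariates | daily morphine equivalents from questionnaires | first 3 weeks |
| Limitations, item 4 | opioid use, said to be a covariate | context is 6 months; no variable defined |

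The accurate statement is that no 6-month opioid covariate is specified.

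**2. Would such a covariate repair the outcome?** No. Opioid use at 6 months is a consequence of the pain, because the protocol makes it so. Adjusting for it conditions on something that the outcome process produced, and the controlled patient is still coded 0.

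**3. Effect on incidence and events.** Under Power analysis and sample size calculation, the plan uses 46 of 259 TKR patients with PPP: 46/259 = 17.8%, which reproduces. Let m be the share of true cases held below 4. The documents give no value, so m is assumed. Observed events = 46 × (1 − m); observed incidence = (46/259) × (1 − m).

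| m (assumed) | Events in 259 | Incidence |
|---|---|---|
| 0% | 46 | 17.8% |
| 10% | 41.4 | 16.0% |
| 20% | 36.8 | 14.2% |
| 40% | 27.6 | 10.7% |
| 50% | 23 | 8.9% |

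**4. Effect on the odds ratio for acute pain.** The same section gives PPP probabilities of 15.5% at mean acute NRS and 30.3% one SD higher. The implied odds ratio per SD is (0.303/0.697)/(0.155/0.845) = 0.4347/0.1834 = 2.37. The section also states 1.24 per point with SD 2.9, which gives 1.24^2.9 = 1.87 per SD and hence 25.5% at +1 SD. The two do not agree, which is a separate matter, so both are carried. With masking m0 at the mean and m1 at +1 SD, each probability becomes p × (1 − m) and the odds ratio is recomputed.

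| Masking pattern (assumed) | m0, m1 | OR from 2.37 | OR from 1.87 |
|---|---|---|---|
| Unrelated to acute pain | 20%, 20% | 2.26 | 1.81 |
| Unrelated to acute pain | 40%, 40% | 2.17 | 1.76 |
| Rises with acute pain | 0%, 20% | 1.74 | 1.40 |
| Falls with acute pain | 20%, 0% | 3.07 | 2.42 |

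For example, the third row in the first OR column uses 0.303 × 0.8 = 0.2424; (0.2424/0.7576)/(0.155/0.845) = 0.3200/0.1834 = 1.74. The fourth uses 0.155 × 0.8 = 0.124; (0.303/0.697)/(0.124/0.876) = 0.4347/0.1416 = 3.07.

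Masking unrelated to acute pain barely moves the odds ratio. Masking related to acute pain moves it substantially, in either direction.

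**The case against.** **Pain under a common analgesic rule is a legitimate outcome.** The protocol says it follows analgesics closely so that 6-month consumption falls within a standard protocol for everyone, and predicting pain under usual care is a fair aim. This stands as a reason to keep the primary endpoint. It does not remove the problem: the rule responds to pain, so it standardises the instruction and not the exposure.

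**The covariate is arguably there.** The generic item has no end date, and the limitations section states the intention outright. A reader might infer that the two sections contradict each other; they do not strictly do so. The fault is underspecification.

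**A reader might infer bias toward the null and a definite loss of power**, on the view that the masked patients are those with the worst course. The documents do not support this. The Significance section says that many patients remain refractory to available therapies. If the severe cases are refractory they stay at 4 or more, the milder ones are masked, and the odds ratio for acute pain is inflated. In addition, the survey behind the 17.8% applied the PPP criteria with no analgesic-free condition stated, so its figures may already be net of some masking; deducting more could count it twice.

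**Opioids may be rare by 6 months.** The outpatient management section weans opioids to an NSAID or COX-2 inhibitor with tramadol as required, and names only NSAID or COX-2 prescriptions at 3 months. This is a fair point on size. It also leaves that section and the continuation paragraph to be reconciled before opioid use at 6 months can be anticipated.

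**Other 6-month measures help.** Raw NRS is lowered by the same treatment. StEP, WOMAC and SF-MPQ-2 add information, but none identifies a patient whose intensity is controlled by opioids.

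**Conclusion.** The point holds on the text. Treatment aims at the value that defines a non-case, the outcome ignores analgesic use, and the covariate relied on has no 6-month definition and could not restore the classification. If any persistent knee pain is held below 4 by opioids at 6 months, its incidence is understated and the models have fewer events, in proportion to the share masked. That share is unknown: the 10-50% range above is illustrative and treats the survey's 17.8% as unmasked.

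No direction of bias in the risk-factor odds ratios, and no power figure, can be given. Both depend on which patients are masked, and a power figure would also depend on which of the two inconsistent planning effects is used. This is a moderate issue that should be fixed; it does not invalidate the primary endpoint as a measure of pain under treatment.

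**What to change.** Leave the analgesic rule and the primary endpoint as they are, and make these changes.

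1. In the Secondary endpoints paragraph, prespecify a labelled sensitivity outcome: NRS of 4 or more, or ongoing opioid use, at 6 months, taken from the 6-month analgesic questionnaire. Define ongoing use, and state in advance whether tramadol counts. Restrict it to use for the operated knee only if indication is recorded; the visit descriptions do not say that it is. Run the Hypothesis 1 and 2 models on this outcome and report them beside the primary results.
2. Make the Covariates paragraph and item 4 of the limitations agree on whether 6-month opioid use enters any model, and do not present adjustment for it as the solution.
3. Reconcile the outpatient text that weans opioids with the paragraph that continues or escalates them. No view is taken here on which is right.

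The cost is one further set of analyses on a questionnaire already scheduled, plus an indication item if the knee-specific version is wanted. There are two downsides to disclose. The composite can over-count patients who take opioids for other pain. Also, because continuation is triggered by an earlier NRS of 4 or more, the composite builds some early pain into the outcome and may inflate its association with acute pain. It is therefore a sensitivity analysis and not a replacement.

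### The planning figures conflict: an odds ratio of 1.24 per NRS point gives 25.5% PPP at mean plus 1 SD, not 30.3%, and at 1.24 the covariate-adjusted power is below 90%

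*Combined protocol and SAP*

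**What the plan says.** The paragraph on power analysis and sample size calculation (under Statistical Analysis) takes its inputs from the sponsor's multi-center survey: 259 TKR patients, 46 of them (17.8%) with PPP at one year. Acute postoperative NRS pain (mean 5.5, SD 2.9) was a significant predictor "with an odds ratio of 1.24 for each 1 point increase in acute postoperative NRS pain" (95% Wald limits 1.098 to 1.390, P=0.0005). For predicted risk the plan then states: "we have an incidence of 15.5% at the mean and 30.3% at the mean plus one standard deviation (NRS=8.4").

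For 90% power at alpha 0.05 without covariates it gives N=130. It continues: "we estimate the multiple squared correlations at 0.5, raising our sample size estimated to 259", and then: "With a 15% dropout rate this values climbs to 298 (round to 300").

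The calculation does not say whether the test is one- or two-sided. Nor does the General statistical analysis section, which speaks only of results "with statistical significance determined with a Type I error threshold of" 0.05. On the range of models, that section says: "Models will be examined with no risk factors, with individual risk factors, and with multiple risk factors". Item 3 of Potential Difficulties and Limitations says: "Although power analysis is based on 17.8% PPP incidence", and reassures the reader: "However our power estimates are conservative and our multivariate analyses are robust and powerful".

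**The concern.** A logistic model with one continuous predictor is fixed by its intercept and slope. Once the risk at the mean, the odds ratio per point and the SD are given, the risk one SD above the mean follows. Here the stated value does not follow, so the plan carries two different effect sizes, and the sample size depends on which one was used.

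The 90% power figure is the only justification given for enrolling 300. The inflation to 259 exists because the main question, in Hypothesis 1, is whether each factor predicts PPP independently of the others. If the survey's own odds ratio is the right planning effect, the adjusted analysis has clearly less power than stated, and a non-significant adjusted predictor could be over-read as evidence of no effect. The Limitations text points the reader the wrong way by calling the estimates conservative.

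**Working it through.** **Inputs.** All are from the power paragraph: odds ratio (OR) 1.24 per point; SD 2.9; risk at the mean p = 0.155; risk at mean + 1 SD 0.303; power 90%; alpha 0.05; squared multiple correlation R² = 0.5; dropout 15%. Sidedness is not given, so both versions are run.

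**1. Do the risks and the OR agree?**
- Slope per SD from the OR: λ = 2.9 × ln 1.24 = 0.624.
- logit(0.155) = −1.696. Then −1.696 + 0.624 = −1.072, a risk of **25.5%**. Rounding in all three inputs moves this only between 25.0% and 26.0%.
- Slope per SD from the risks: logit(0.303) − logit(0.155) = −0.833 + 1.696 = 0.863. Per point this is exp(0.863/2.9) = **1.347**.
- 1.347 lies inside the reported interval (1.098 to 1.390) but is not the reported estimate.

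**2. Can the plan's 130 be reproduced?** The plan names a SAS macro but gives no formula. Two standard ones were tried:
- Hsieh 1989: N = (z_α + z_β e^(−λ²/4))² (1 + 2pδ)/(pλ²), with δ = [1 + (1+λ²)e^(5λ²/4)]/[1 + e^(−λ²/4)].
- Hsieh-Bloch-Larsen (HBL): N = (z_α + z_β)²/[p(1−p)λ²].

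Both are divided by (1 − R²) for covariates. N for 90% power at p = 0.155:

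| Effect | Formula | One-sided, R²=0 | Two-sided, R²=0 | One-sided, R²=0.5 | Two-sided, R²=0.5 |
|---|---|---|---|---|---|
| 30.3% (λ=0.863) | Hsieh 1989 | 122 | 152 | 244 | 304 |
| 30.3% | HBL | 88 | 108 | 176 | 216 |
| OR 1.24 (λ=0.624) | Hsieh 1989 | 200 | 247 | 400 | 495 |
| OR 1.24 | HBL | 168 | 206 | 336 | 412 |

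None gives 130. The nearest is 122 (Hsieh, one-sided, 30.3% input), about 6% lower. The R² step itself is consistent: 130/0.5 = 260, against 259.

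**3. Power at OR 1.24 with R² = 0.5** (p = 0.155):

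| Method | Two-sided, n=255 / 259 | One-sided, n=255 / 259 |
|---|---|---|
| Hsieh 1989 | 62.2% / 62.9% | 74.5% / 75.1% |
| HBL | 72.2% / 72.9% | 81.7% / 82.2% |
| Simulation (Wald test, one covariate, 20,000 runs) | 72.2% / 72.2% | 81.8% / 82.1% |

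The simulation supports HBL. With p = 0.178 instead, the best case is 86% (HBL, one-sided, n=259), and 90% power still needs 301 to 453 evaluable.

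**4. Sensitivity.**
- Two-sided power at 255 for OR 1.24 is 91% to 95% with R² = 0 and 83% to 90% with R² = 0.2.
- The largest R² that keeps 90% at 255 is 1 − N/255, with N taken at R² = 0. Two-sided this is 0.03 (Hsieh) or 0.19 (HBL); one-sided, 0.22 or 0.34. The plan assumes 0.5.
- If 30.3% is right, two-sided power at 255 to 259 with R² = 0.5 is 84% (Hsieh) or 94% (HBL; simulation 94%).

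**5. Dropout.** 259 × 1.15 = 297.9, the plan's 298. To keep 259 after 15% loss takes 259/0.85 = 304.7, so 305. Enrolling 300 leaves 300 × 0.85 = 255.

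**The case against.** The strongest reply is that the shortfall is conditional. If 30.3% reflects the effect the sponsor meant to detect, the implied 1.347 is within the survey's confidence interval, and power at 255 is about 94% by the formula that simulation supports. This stands, and it is why the sponsor must say which effect is the target. There is also evidence on the other side: the geometric centre of the reported interval is √(1.098 × 1.390) = 1.235, and its width implies P of about 0.0004, close to the stated 0.0005. The OR, interval and P value therefore fit together, and the 30.3% is the figure that does not fit. That does not prove it is the error, because the SD or a different underlying model could also explain the gap.

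The failure to reproduce 130 is weak evidence by itself, since the macro's formula and sidedness are not given. It supports a request to state the method.

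The lower end of the power range (62% to 63%) comes from the Hsieh 1989 formula, which the simulation does not support. The better-supported figures are 72% two-sided and 82% one-sided.

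R² = 0.5 is a guess, and backward selection may retain fewer covariates. True, but it is the assumption on which the plan bases its 259.

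The 17.8% and 15.5% do not contradict each other: one is overall incidence, the other risk at the mean NRS, and the overall figure is expected to be higher. What remains is that the Limitations section names 17.8% as the basis of the power analysis, so the input used should be stated.

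**Conclusion.** The concern holds. Within a single logistic model, OR 1.24 per point, SD 2.9 and 15.5% at the mean give 25.5% at NRS 8.4, and rounding cannot bridge the gap to 30.3%. If 1.24 is the right effect, the covariate-adjusted analysis does not have 90% power at 255 to 259 evaluable under either formula, either sidedness or either event rate. It has 62% to 82% at 15.5%, and at most 86% at 17.8%.

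This rests on the plan's own R² of 0.5, an approximately normal NRS predictor and an unadjusted alpha of 0.05. It does not touch the single-factor models, which keep at least 90% at 255. The dropout slip is real but minor. This should be corrected; it does not call for a larger study.

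**What to change.** Keep N=300 and revise the text:

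1. Check the survey output and reconcile OR 1.24, 15.5% and 30.3%. Either correct 30.3% to 25.5%, or state and justify about 1.35 per point as the target effect.
2. State the sidedness, the formula and the event rate used, and rerun the calculation.
3. State that 300 enrolled with 15% dropout leaves 255 evaluable.
4. Restate power, or the detectable OR, from that one formula. For example, HBL with 15.5%, R² = 0.5 and 255 evaluable gives, two-sided, 72% power for OR 1.24 or a detectable OR of about 1.315 at 90%; one-sided, 82% or about 1.28. These use alpha 0.05 without the step-down Bonferroni correction in General statistical analysis. If that correction covers the risk factors, power at its strictest step is lower: about 49% for two-sided HBL at OR 1.24, assuming five factors.
5. Remove the statement in Potential Difficulties and Limitations that the power estimates are conservative.

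The cost is a text change and one rerun of the power calculation. No extra patients are needed. The stated power will probably become less favourable.
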